9.5.6 Pharmacokinetics Analysis

PK analysis will be carried out for subjects in the dose-escalation study and in the efficacy study with blood samples collected at defined timepoints as listed in section 1.3. The PK analysis will be PP. The following PK analysis will be performed as needed.

Individual Subject Pharmacokinetic Analysis: A non-compartmental (NC) PK analysis will be performed on the L9LS concentration data generated from each subject. Individual subject and dosing arm concentration-versus-time profiles will be constructed in linear and semi-log scales. In the NC analysis, the maximum concentration (Cmax) and time of maximal concentration (Tmax) will be taken directly from the observed data. The area under the concentrations vs. time curve (AUC) will be calculated using the trapezoidal method and determined out to the final concentration collected. If a subject's L9LS concentration falls below the quantitative limit (QL) of the assay, the sample with concentration below the QL will be assigned a L9LS concentration value of "0" for AUC calculations. In addition to the total AUC, partial AUCs will also be determined over certain time intervals. The time-weighted average concentrations (Cave) during these intervals will be calculated as the AUC divided by the AUC collection interval (e.g., Cave₀- $_{16\text{WK}} = (\text{AUC}_{0\text{-}16\text{WK}}) / 16 \text{ weeks}$). The terminal slope, \Box_z , will be determined by regression of the terminal, log-linear portion of the concentration-versus-time profile. If the final PK sample has measurable L9LS concentrations greater than the assay QL, the AUC post-final PK collection (AUC_{last-infinity}) will be estimated as C_{last} / \Box_z and AUC_{0-infinity} will be calculated as the sum of $AUC_{0-last} + AUC_{last-infinity}$.

Population Pharmacokinetic Analyses: Based on preclinical PK results for L9LS and known PK behavior studies of MAbs, the two-compartment model will be used for population PK analysis. The population analysis will estimate compartmental PK parameters such as the clearance (CL), central and peripheral volumes of distribution (Vd1 and Vd2), and intercompartmental clearance (Q). Total volume of distribution at steady-state (Vdss), will be calculated as the sum of Vd1 + Vd2. Alpha and beta half-lives will be calculated from CL, Q, Vd1, and Vd2 using standard equations. ³⁸

Version Date: 14 March 2024

To assess the association of L9LS concentration with protection, we will perform a Cox proportional hazards regression for the time to the first infection with L9LS concentration as a time-varying covariate. A logistic regression analysis will be additionally performed to model the infection rate as a function of L9LS concentration via the method of generalized estimating equation (GEE) to account for repeated measures. The GEE estimation will only be performed over the scheduled visits with the binary outcome (infected or not) as the response and the L9LS concentration as the covariate. This analysis will be performed over all participants that receive L9LS including those aged 6-10 years in the dose-escalation study and those in the efficacy study.

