The first part of the study is an age de-escalation and dose-escalation study for safety and tolerability. Adult subjects (N=18) in the dose-escalation study will be assigned in open-label fashion to 1 of 3 L9LS dose arms (n=6 for each dose level). Dosing will begin in the lowest dose arm (300 mg SC). Once all subjects in that arm reach day 7 post-administration, if no safety concerns have arisen, dosing will begin at the next dose level (600 mg SC). Once all subjects in that arm reach day 7 post-administration, if no safety concerns have arisen, dosing will begin at the highest dose level (20 mg/kg IV). Once all adult subjects reach day 7 post-administration, if

Version Date: 14 March 2024

no safety concerns have arisen, 18 subjects aged 6-10 years will be randomized 1:1 in double-blind fashion to 150 mg of L9LS versus placebo administered SC. Once all 18 subjects reach day 7 post-administration, if no safety concerns have arisen, an additional 18 subjects aged 6-10 years will be randomized 1:1 to 300 mg of L9LS versus placebo administered SC. Randomization of subjects aged 6-10 years in each L9LS dose arm will be weight-stratified (26-30 kg, n=6; 20-25 kg, n=6; 15-19 kg, n=6) and enrollment will be weight de-escalated starting with subjects weighing 26-30 kg. All subjects will be followed for safety to assess AEs at study visits over 28 weeks. Primary study assessments include medical history, physical examination and blood collection for identification of Pf infection and other research laboratory evaluations. After the last 6-year-old subject in the 300-mg L9LS arm reaches day 7 safety follow-up, an interim safety evaluation will be performed before enrollment begins for the efficacy part of the study. Data from the 36 subjects aged 6-10 years enrolled in the dose-escalation study will be included in a secondary analysis to determine the relationship between L9LS concentrations and the risk of Pf infection. For these 36 subjects, blinding will be maintained for treatment assignment (L9LS versus placebo), but not for possible L9LS dose group.

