7.3 Missed Visits and Lost to Follow-up

If a participant misses 1 visit after D28 or 2 visits after D28 that are not sequential, these will not be considered protocol deviations. However, 2 missed visits in a row or a total of 3 or more missed visits (regardless of whether or not they are sequential) over the duration of the study will be considered protocol deviations.

A subject will be considered lost to follow-up if he or she fails to return for 3 consecutive scheduled visits and is unable to be contacted by the study site staff.

The following actions must be taken if a subject fails to return to the clinic for a required study visit:

- The site will attempt to contact the subject/parent/guardian and reschedule the missed visit within 7 days, counsel them on the importance of maintaining the assigned visit schedule, and ascertain if they wish to and/or should continue in the study. If a missed visit cannot be rescheduled, the participant may continue with the next scheduled visit.
- Before a subject is deemed lost to follow-up, the investigator or designee will make every effort to regain contact with the subject/parent/guardian (where possible, 3 telephone calls). These contact attempts should be documented in the subject's medical record or study file.
- Should the subject/parent/guardian continue to be unreachable, he or she will be considered to have withdrawn from the study with a primary reason of lost to follow-up.

Version Date: 14 March 2024

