9.4 Populations for Analyses

The following datasets will be considered in study analyses:

• Intention-to-treat (ITT) analysis dataset will include all subjects that receive assignment and will be analyzed according to the initial randomization assignment.

Version Date: 14 March 2024

Modified intention-to-treat (MITT) analysis dataset will include all randomized subjects
that receive the study intervention and will be analyzed according to the initial
randomization assignment.

 Per-protocol (PP) analysis dataset will include all randomized subjects that receive the study intervention consistent with the initial randomization assignment and complete the scheduled visits, and will be analyzed according to the initial randomization assignment.
 In cases where subjects receive an intervention other than the one randomly assigned, an as-treated analysis will be additionally performed according to the actual product received.

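### The per-protocol rule for the PK analysis leaves out all 18 non-randomized adults and ties children's PK to visits at which no PK sample is drawn

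*Combined protocol and SAP*

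**What the plan says.** Section 9.5.6 opens by setting the scope: "PK analysis will be carried out for subjects in the dose-escalation study and in the efficacy study with blood samples collected at defined timepoints". It then names the analysis set: "The PK analysis will be PP". Section 9.4 defines the per-protocol (PP) set as "all randomized subjects that receive the study intervention consistent with the initial randomization assignment and complete the scheduled visits". It gives no attendance threshold and does not mention PK samples.

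Section 4.1 describes the adults differently from the children: "Adult subjects (N=18) in the dose-escalation study will be assigned in open-label fashion to 1 of 3 L9LS dose arms". Secondary objective 1 (sections 1.1 and 3) asks for PK at 300 mg and 600 mg SC and 20 mg/kg IV in adults, as well as at the two pediatric doses.

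The last paragraph of section 9.5.6, on concentration and infection risk, names a different set: "This analysis will be performed over all participants that receive L9LS including those aged 6-10 years in the dose-escalation study".

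Section 7.3 says of attendance: "If a participant misses 1 visit after D28 or 2 visits after D28 that are not sequential, these will not be considered protocol deviations". Section 9.5.1.1 applies the Year 1 PK methods to the extension, where measurement of L9LS in serum is a primary endpoint.

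**The concern.** A PK set should be built on exposure and usable samples. The rule here is built on randomization and attendance, and neither fits this trial.

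Randomization is the wrong gate because one part of the trial has none. If the rule is followed as written, two regimens named in a secondary objective have no analysable subjects, and the trial's only intravenous data drop out.

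Attendance is the wrong gate because most scheduled visits carry no PK sample. A child with every planned concentration could be removed for missing a visit that would have added none. The planned methods do not need full attendance: AUC is calculated to the last concentration collected, and a two-compartment population model can use partial profiles. Precision would be lost for no methodological gain, in an analysis that supports a primary endpoint of the extension.

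**Working it through.** No PK sample size or exclusion count is stated in the plan, so there is no figure to reproduce. The check compares the passages, counts visits, and then illustrates the loss under stated assumptions.

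**Adults.** Table 1 gives 6 adults at 300 mg SC, 6 at 600 mg SC and 6 at 20 mg/kg IV: 6 + 6 + 6 = 18. Section 1.1 restricts the last two regimens to adults. PP admits randomized subjects only, so by its wording 0 of 18 adults are in the set. No missed-visit rate enters this result.

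**Visits with and without a PK draw** (schedules in sections 1.3.3 and 1.3.4, after day 0):

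- Efficacy study: days 1, 3, 7, 14, 21 and 28, then every 14 days from 42 to 168, which is 16 visits. PK is drawn on days 7, 28, 56, 84, 112, 140 and 168, which is 7. Without a draw: 16 − 7 = 9.
- Extension: the same days, plus 182, 196, 224 and 252, which is 20 visits. PK is drawn on days 7, 28, 84, 140, 196 and 252, which is 6. Without a draw: 20 − 6 = 14.

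**Possible loss in children.** Let m be the chance of missing any one visit, independent across visits. The documents give no value, so m is an assumption. If all k counted visits must be attended, the excluded share is 1 − (1 − m)^k. For the section 7.3 tolerance, a child is excluded for two misses in a row or three or more in total among the visits after day 28 (10 in the efficacy study, 14 in the extension). That probability was obtained by enumerating all attendance patterns.

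| Reading of completing the visits | Efficacy, m = 2% | Extension, m = 2% | Efficacy, m = 5% | Extension, m = 5% |
|---|---|---|---|---|
| Every post-dose visit (k = 16; 20) | 1 − 0.98^16 = 28% | 1 − 0.98^20 = 33% | 56% | 64% |
| PK visits only (k = 7; 6) | 1 − 0.98^7 = 13% | 1 − 0.98^6 = 11% | 30% | 26% |
| 7.3 tolerance, and any miss through day 28 excludes | 12% | 12% | 28% | 30% |
| 7.3 tolerance, post-day-28 misses only | 0.4% | 0.7% | 3% | 5% |

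At m = 1% the first row becomes 15% and 18%. If misses cluster within children, fewer children are affected than independence implies. On the strictest reading at m = 2%, an extension arm of 42 keeps 42 × 0.98^20 = 28 children.

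**Dropout.** Section 9.2.2 plans for 10% dropout. L9LS children in Year 1 number 75 + 75 + 9 + 9 = 168. If that rate applied to them, 168 × 0.9 = 151 would remain, so about 17 would leave the set even if their earlier samples were usable.

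**A second uncertainty about PP.** Section 9.4 analyses PP subjects by initial assignment. Section 9.5.5 describes a per-protocol analysis by product actually received. The set named for PK therefore has two descriptions.

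**The case against.** The best case for the plan is that this is loose drafting with a clear intent. Section 9.5.6 says PK covers the dose-escalation study and the objectives name the adult doses, so nobody means to omit the adults. The attendance condition has no threshold, and section 7.3 can supply one: a child with no deviation stays per-protocol. Section 7.3 also allows a missed visit to be rescheduled within 7 days. On the mildest reading above, the loss in children is negligible. The PK analysis is also largely descriptive and has no power claim.

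Much of this stands for the children. The defect there is an undefined condition, and the large exclusion figures belong to its strictest reading. It does not rescue the adults: the intent to include them is plain, but the named set does not admit them. Nor does it justify attendance as a criterion for PK.

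Two stronger readings are tempting. A reader might infer that section 9.5.6 contradicts itself because the concentration-risk analysis uses all L9LS recipients. The documents do not support that: the paragraph names its own set and can be read as a specific exception to a general sentence. The two statements are unreconciled, since no exception is declared. A reader might also infer that selecting on attendance selects on illness or infection. That is possible but not shown. Infected children stay in follow-up, and illness visits are additional to the schedule.

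**Conclusion.** The point holds in a limited form. The firm part is that the PP set as defined contains none of the 18 adults, so 600 mg SC and 20 mg/kg IV have no subjects in the named PK set. This rests only on the wording of sections 4.1, 9.4 and 9.5.6.

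The softer part is that the set makes children's PK depend on attendance at visits without a PK draw. The resulting loss is unknown. At an assumed 2% miss per visit it runs from under 1% to 28% in the efficacy study and from under 1% to 33% in the extension, depending on how completion is read; the independence of misses is also assumed. The primary efficacy test is unaffected. The matter should be corrected because it touches a secondary objective and a primary endpoint of the extension.

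**What to change.** Replace the PP sentence in section 9.5.6 with a defined PK set:

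- Include every L9LS recipient, adults named explicitly, with at least one evaluable post-dose concentration, analysed by product and dose actually received.
- State the minimum sampling needed for each non-compartmental parameter.
- Use all valid samples in the population model, and drop only individual samples with documented dosing or sampling errors.
- Keep PP as a sensitivity analysis, and say what completing the scheduled visits means for it.
- State that the concentration-risk analysis uses all L9LS recipients, as its own paragraph already says.
- Apply the same set to the extension through section 9.5.1.1.

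No new visits or samples are needed. The cost is a protocol amendment, since the statistical section is part of the protocol and amendments need ethics committee approval, and some incomplete profiles in the non-compartmental summaries. Year 1 unblinding was planned for about March/April 2023 and this version is dated 14 March 2024. A Year 1 change should therefore be dated and explained, with the PP results shown alongside.

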9.5.7 Baseline Descriptive Statistics

Treatment arms will be compared for baseline subject characteristics using descriptive statistics. For continuous variables, the mean or median will be calculated for each treatment arm. For categorial variables, the proportion under each category will be calculated for each arm.

9.5.8 Planned Interim Analyses

Interim safety analysis will be performed when safety data are available from the age deescalation and dose-escalation study subjects. The purpose of the interim analysis on safety data is to clear safety concerns for proceeding to the efficacy study. This interim analysis will not affect the power or type I error in the primary analysis on efficacy in the efficacy study.

9.5.9 Sub-Group Analyses

Not applicable.

9.5.10 Tabulation of individual Participant Data

Safety data will be presented by line listing and tables at the individual level, as described in section 9.5.5.

9.5.11 Exploratory Analyses

To explore the impact of L9LS on the genotype of infection-inducing parasites at the CSP locus, a genotypic sieve analysis will be performed to analyze CSP sequences of breakthrough parasites in the blood samples of infected subjects. The sieve analysis will differentiate protective efficacy against different genotypes of infection-inducing parasites with genotype defined by, for example, number of mismatches to the L9LS footprint.

For assessment of ADA in the year 2 extension study, the count and percentage (as well as the exact 95% CI) of participants with detectable ADA in each arm will be reported. The percentage of participants with detectable ADA will be compared between two arms via Fisher's exact test.

Version Date: 14 March 2024

10 REGULATORY AND OPERATIONAL CONSIDERATIONS

10.1 Informed Consent Process

10.1.1 Consent Procedures and Documentation

The informed consent process for this study will involve obtaining initial community permission followed by individual informed consent.

10.1.1.1 Community Permission for the Conduct of the Study

Prior to the start of this study, community permission will be obtained as described in section 5.7. Following the process of Diallo and colleagues, ³⁹ the community permission process will involve the following:

- 1. Study investigators/personnel explain the study to village leaders, including the village chief, family heads, women association, and elders.
- 2. The village leaders discuss the study with family heads and community members and relay any additional questions or concerns to the study personnel.
- 3. The study and the informed consent process are explained in detail to heads of families by study investigators/personnel.

10.1.1.2 Individual Informed Consent

Consent process: The study informed consent form will be written in French. The study team will review the consent form word-for-word and will translate it orally into local languages, since most potential study subjects and minor subjects' parents/guardians do not read or speak French. An independent witness who is not a member of the study team will verify that oral translations are accurate and that potential adult subjects and parents/guardians of minor subjects understand the contents of the consent form.

Local households and families will be invited to come to the study clinic for review of the informed consent. At the consenting visit, the adult subject or minor subject's parent/guardian will read the consent form or have it explained to them (in cases of illiteracy). Individuals in each family will be separately consented, and not all individuals from a household need to participate. Adult subjects will provide consent by signing or fingerprinting (if illiterate) the consent form. Parents/guardians will provide permission for their child/ward to participate by signing or fingerprinting (if illiterate) the consent form.

Also, a study comprehension examination will be conducted to make sure that the study is understood by the potential adult subject or minor subject's parent/guardian prior to signing consent. The exam will be written in French and translated orally into local languages. All incorrect responses will be reviewed, and individuals must orally confirm their understanding of all incorrect responses. A score of at least 80% correct responses by the potential adult subject or

Version Date: 14 March 2024

by the parent/guardian is mandatory to enroll the adult or their child/ward, respectively. For individuals scoring below 80%, study staff may choose to review study details again and reassess comprehension by repeating the examination. At the discretion of the investigator, any potential adult subject whose comprehension is questionable, or the child/ward of any individual whose comprehension is questionable, regardless of score, may be excluded from enrollment.

Minor participants will be included in all discussions about the study, and age-appropriate language will be used to describe the procedures and tests involved in this study, along with the risks, discomforts, and benefits of participation. However, children will not be required to provide assent as the age ranges included in this study typically do not have the ability to fully understand the nature of research.

The consent process will be documented in the adult or child subject's medical record.

10.1.2 Consent for Minors When They Reach the Age of Majority

When a pediatric subject reaches age 18, continued participation (including ongoing interactions with the subject or continued analysis of identifiable data) will require that consent be obtained from the now adult with the standard protocol consent document to ensure legally effective informed consent has been obtained.

If reconsent is not feasible, we request waiver of informed consent to continue to use data and/or specimens for those individuals who become lost to follow up or who have been taken off study prior to reaching the age of majority.

Requirements for Waiver of Consent consistent with 45 CFR 46.116(f)(3):

- (1) The research involves no more than minimal risk to the subjects.
 - a. Analysis of samples and data from this study involves no additional risks to subjects.
- (2) The research could not practicably be carried out without the waiver or alteration.
 - a. Considering the length of time between the minor's last contact with the research team and their age of majority, it will likely be very difficult to locate them again. A significant reduction in the number of samples analyzed is likely to impact the quality of the research.
- (3) As the research involves using identifiable private information or identifiable biospecimens, the research could not practicably be carried out without using such information or biospecimens in an identifiable format.
 - a. Though the purpose of future studies cannot yet be known, they often involve the correlation of clinical outcomes and clinical interventions with laboratory studies. Such information would be unavailable if access to medical record numbers was unavailable.

Version Date: 14 March 2024

(4) The waiver or alteration will not adversely affect the rights and welfare of the subjects.

- a. Retention of these samples or data does not affect the welfare of subjects.
- (5) Whenever appropriate, the subjects will be provided with additional pertinent information after participation.
 - a. We only request a waiver of consent for those subjects who have been lost to follow-up or who have been taken off study prior to reaching the age of majority.

10.2 Study Discontinuation and Closure

The study may be temporarily suspended or permanently terminated as described in the halting rules (section 8.4.6). In addition to the reporting described in that section, the principal investigator(s) will promptly contact the study subjects, provide the reason(s) for the termination or suspension, and, if applicable, inform them of changes to study visit schedule.

The principal investigators will consult with the EC prior to resuming the study following a halt.

